**The Effect of The Mobile Application on Treatment Adherence, Self-Management, and
Quality of Life in Patients with Acute Myocardial Infarction Undergoing Primary
Percutaneous Coronary Intervention**

[name], [name],

[name], Msc, RN, Research Assistant (Corresponding author)

Department of Nursing, Trakya University Faculty of Health Sciences, Edirne, TURKIYE

Orcid No: [name]

e-posta: [contact]

[name] [name], Msc, RN, Associate Professor

Department of Nursing, Trakya University Faculty of Health Sciences, Edirne, TURKIYE

Orcid No: [name]

e-mail: [contact]

Address for Correspondence:

[name], Msc, RN, Research Assistant

Address: [name]

[contact]

[contact]

e-mail: [contact]

Background and Aim: Acute myocardial infarction is a clinical condition with high mortality and morbidity rates. Ensuring patient adherence to treatments and lifestyle recommendations after discharge is crucial for effective post-acute myocardial infarction management. This study aimed to determine the impact of the mobile application on treatment adherence, self-management, and quality of life in patients with acute myocardial infarction undergoing primary percutaneous coronary intervention.

Study's Methods

Study design and sample

The study was conducted as a prospective (6-month follow-up), two-group (control and intervention), randomized controlled, experimental study.

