The universe of the study consisted of patients who had their first time ST segment elevation MI (STEMI) undergoing PPCI in the Cardiology Clinic of a university hospital in Edirne, Turkey, between 01.11.2021 and 10.07.2024. In determining the sample of the study, power analysis was performed with reference to the study of Turan Kavradım and Özer (68). The effect size of the study was found to be 0.92 and considering this effect size, it was determined that it was sufficient to include a total of 54 patients, 27 in each group, at 95% power and 0.05 significance level. However, considering a 20% loss rate during the study period (30), it was aimed to reach a total of 66 patients, 33 patients for each group. Patients who volunteered to participate in the study were determined in accordance with the inclusion criteria. The selection of patients to the intervention and control groups was made using the simple randomization method. According to the randomization list, the groups were matched based on the time of discharge from the clinic of the patients. For patients who were discharged on the same day, the matching was based on their hospitalization times. The inclusion criteria were as follows: the patients who (1) had first time STEMI undergoing PPCI, (2) are over 18 years of age, (3) have a smartphone, (4) have internet access, (5) have orientation to place, time and situation, (6) have no problems with vision, hearing and speech, (7) are at least literate, (8) regularly come in for the doctor's check up, and (9) volunteer to participate in the study. Among the volunteers participating in the study, those who wanted to leave the study (2 patients) and those who didn't come in for the doctor's check up (3 patients) were excluded from the follow-up. Therefore, the study was completed with 61 patients, 30 in the intervention group and 31 in

the control group. The study design and implementation were based on the principles in the CONSORT (Consolidated Standards of Reporting Trials) list (Figure 1).

[figure not shown]

Figure 1. Flow chart of design and recruitment of participants according to CONSORT statement

Study Protocol

Education booklet

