In the third stage, a web page control panel was created that allows the mobile application to be controlled remotely, patient information to be viewed, data to be monitored, lifestyle information to be uploaded and viewed in the mobile application, personalized reminders to be sent to patients, and to be communicated with patients (<https://www.medicoll.com/>, <https://www.medicoll.com/brave/login>).

In the fourth phase, the application was purchased from Google Play Store and App Store. In the fifth stage, the mobile application and website were tested by experts for 1 week to determine usability of them and errors. Finally, a pilot study was conducted with 4 patients and the patients were allowed to use the application for a month. Patients who participated in the pilot study were not included in the study.

After the pilot study was completed, the Patient Information Form was filled out with all patients in the patient room before discharge. The researcher provided training to the patients in both groups in line with the education booklet and it was delivered to the patients. MEDIFOLL application was downloaded to the mobile phones of the patients in the intervention group and user registration was made. Information was provided to them on how to use the application and how to enter data such as blood pressure and pulse rate. The times of the use of medications prescribed during discharge were planned together with the patients and they were provided with the opportunity to enter their medications into the application.

Patients in the intervention and control groups were interviewed in the outpatient clinic 1 month, 3 months and 6 months after discharge, and the Patient Information Form, IUBÖ ve MIDAS scales were filled out. The flow chart of the research is presented in Figure 2.

Determination of the content of “Educational Booklet for Patients Who Have Had a Heart

Obtaining expert opinion for the educational booklet and developing the booklet

[figure not shown]

Figure 2. The flow chart of the research

Data collection tool

Patient Information Form: It, developed by the researcher through a literature review (15,18,30,36,59,67), consists of questions about the socio-demographic, the lifestyle, and the disease characteristics of the participants.

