Medical Adherence Report Scale (MARS): The scale was developed by Horne and Hankins to determine medication adherence in individuals with chronic diseases. The Turkish validity and reliability of the scale was performed by Şen et al. (21). The scale has 5 items, one sub-dimension and 5-point Likert type. The total score obtained from the scale varies between 5 and 25. A high total score indicates adherence to medication treatment, while a low score indicates non-adherence to medication treatment. The Cronbach alpha value of the scale was found to be 0.78 in the study of Şen et al. (21) and 0.68 in this study.

Myocardial Infarction Dimensional Assessment Scale (MIDAS): The Turkish validity and reliability of the scale, developed by Thompson et al., was performed by Yılmaz et al. (71). The scale is used to determine the HRQoL of individuals with MI and consists of 35 items and 7 sub-dimensions (physical activity, insecurity, emotional reaction, dependency, diet, concerns over medication, and medication side effects). This 5-point Likert-type scale is scored between 0-4. Scores that can be obtained from the scale and its sub-dimensions vary between 0-100. The score is calculated with the formula: (Total score obtained from the sub-dimension/highest score that can be obtained from the sub-dimension) x100. As the scores obtained from the scale increase, the perceived HRQoL worsens. In the study of Yılmaz et al. (71), the Cronbach alpha value of the sub-dimensions of the scale was found to be between 0.79-0.90. In this study, it was found to be 0.93.

Ethical Consideration

The study was conducted in accordance with the Declaration of Helsinki. The study protocol was approved by the Scientific Research Ethics Committee of XXX University Faculty of Medicine (xxx), and written permission was obtained from the institution where the study was to be conducted (xxx). Necessary written consents were obtained from the patients.

Data Analysis

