The data were evaluated using the IBM SPSS 22.0 (Statistical Package for Social Sciences 22.0) package program. The data to a normal distribution was examined by the Kolmogorov–Smirnov test. The number and percentage distribution were used to evaluate categorical data, and meanstandard deviation was used to evaluate continuous data. In the analysis of the data, Mann Whitney U test was used to compare the mean scores that did not show normal distribution between the groups and Student's t test was used to compare the mean scores that showed normal distribution. Pearson chi-square test and Fisher-Freeman-Halton Exact test analysis

were used to determine the relationship between groups for nominal variables. The statistical significance limit value was accepted as $p<0.05$.

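### Scores are collected at 1, 3 and 6 months, but the plan gives no between-group difference with a confidence interval and no analysis that uses the visits together

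*Combined protocol and SAP*

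**What the plan says.** Background and Aim states the purpose: "This study aimed to determine the impact of the mobile application on treatment adherence, self-management, and quality of life". Under Study Protocol, patients in both groups "were interviewed in the outpatient clinic 1 month, 3 months and 6 months after discharge", and at those visits the "IUBÖ ve MIDAS scales were filled out". The abbreviation IUBÖ is not defined. By elimination it appears to be the adherence scale that Data collection tool calls MARS. MIDAS "consists of 35 items and 7 sub-dimensions", and the scale as a whole is also scored.

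The Data Analysis section covers scores in three steps. First, "The data to a normal distribution was examined by the Kolmogorov–Smirnov test". Next, the mean and standard "deviation was used to evaluate continuous data". Last comes a between-group test: Student's t for scores judged normal, and for the rest "Mann Whitney U test was used to compare the mean scores that did not show normal distribution between the groups". The chi-square and Fisher-Freeman-Halton tests are for nominal variables. The section names no between-group difference, confidence interval, repeated-measures or mixed model, group-by-visit term or summary over visits, and no other section supplies one.

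**The concern.** Impact is a quantity. A test result does not give its size, and the plan asks for no estimate of the difference and no interval around one. The follow-up has three visits, yet no planned analysis can say whether a difference grows, holds or shrinks between month 1 and month 6.

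If the tests are run visit by visit, as seems likely, the output is a row of p values. When some fall below 0.05 and others do not, it is natural to read the effect as appearing or fading. A constant effect produces the same pattern. Conversely, a non-significant visit may be read as no effect when the data remain compatible with the effect the trial was sized to find.

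The normality-based choice adds a smaller problem. The Mann-Whitney test does not compare means, although the text says it does, so different scores or visits could be tested on different quantities.

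**Working it through.** **Inputs from the documents.** Visits at 1, 3 and 6 months (Study Protocol); 30 intervention and 31 control completers (Study design and sample); planned standardised effect, "The effect size of the study was found to be 0.92" (same section); significance level 0.05 (Data Analysis). The documents give no SD and no between-visit correlation r, so results are in SD units and r is assumed. The formulas take the SD and the correlation as equal across visits.

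**The plan's own figure.** For an effect of 0.92, 95% power and level 0.05, a one-sided two-sample t test needs 27 per group (power 95.5%), which matches the stated 54. Two-sided, 27 per group gives 91.3%, and 30 v 31 gives 94.2%. Either way the sample size rests on one two-sample comparison and does not use the three visits. This point disputes no stated figure.

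**Interval at one visit.** Half-width = t(0.975, 59 df) × √(1/30 + 1/31) = 2.001 × 0.2561 = 0.512 SD.
- An observed difference of 0.92 would have the interval 0.92 ± 0.512 = 0.41 to 1.43.
- An observed difference between 0.92 − 0.512 = 0.41 and 0.51 is non-significant, yet its interval still includes 0.92.

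**Intervals that use the visits together.** Visit average: 0.512 × √((1 + 2r)/3). Change in the difference from month 1 to month 6: 0.512 × √(2(1 − r)).

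| r (assumed) | Visit average, ±SD | Change, month 1 to 6, ±SD |
|---|---|---|
| 0.3 | 0.374 | 0.606 |
| 0.5 | 0.418 | 0.512 |
| 0.7 | 0.458 | 0.397 |
| 0.9 | 0.495 | 0.229 |

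**What a reader can rebuild without r.** The standard error of an average never exceeds the average of the per-visit standard errors, so ±0.51 SD is safe for the visit average at any r. For the change, if r is not negative, the limit is 0.512 × √2 = ±0.72 SD. Both are valid but conservative.

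**Mixed significance under a constant effect.** Simulation: 40,000 trials per setting, normal scores, 30 v 31, equal correlation, two-sided 0.05. Mixed means that one or two of the three visit t tests are significant. With 0.92 at every visit, the pattern is mixed in 13.1% of trials at r = 0.5 and 10.6% at r = 0.7; repeat runs gave 10–13%. A group-by-visit test (2 df) is significant in 4.9% and 5.0%, as it should be when the effect does not change.

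**What the joint analysis cannot do.** With an assumed effect building 0.2, 0.35, 0.5, the group-by-visit test has 15.9% power (r = 0.5) or 24.1% (r = 0.7). The 6-month test has about 48%, and the visit average 37.7% or 32.6%.

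**The case against.** The best defence is that the planned tests are legitimate two-sample comparisons and that published means and SDs by group and visit would let anyone compute a per-visit interval. That is right. A reader might infer that no interval for the visit average or the change could be recovered at all. That goes too far, since conservative ones are available. The loss is in reporting and precision.

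Several other strong readings also lack support:
- The text does not say that tests are run visit by visit; that is an inference. Nor does it claim that an effect appears or fades.
- No inflation of the per-visit type I error is shown, and how often the normality check would pick different tests at different visits cannot be determined from the documents.
- Mixed patterns might be presented as the usual outcome. At a constant effect of 0.5 they occur in 38–50% of simulated trials, but 0.5 is assumed, about half the planned value. At 0.92 all three visits are significant in about 86–88%. Even 0.92 is not tied to a scale or visit in the documents.

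It can also be said that a mixed model barely helps. With complete data it gives the same per-visit differences, leaves any mixed pattern in place and has low power to detect change. Nor does it settle which score or visit is primary. All of this stands, but it does not remove the gap: an effect size, an interval and a valid test of change are still missing from the plan, and the data to supply them have been collected.

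**Conclusion.** The point holds as a limitation of estimation and interpretation; it does not invalidate the planned tests. For an aim stated as impact, the plan provides neither a between-group difference with a confidence interval nor any analysis joining the three visits.

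The per-visit half-width of 0.51 SD follows from the group sizes alone. Sharper intervals for the visit average and the change need the within-patient correlation, which only the sponsor can estimate; the gain over the conservative versions depends on that correlation. The 10–13% rate of mixed significance assumes normal scores, a correlation of 0.5–0.7 and an effect of 0.92 at every visit; it would be higher for a moderately smaller effect. The change should be made, because it is cheap and uses existing data.

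**What to change.** Replace the normality-based choice of test. For MARS, MIDAS total and each reported MIDAS sub-dimension (1 + 1 + 7 = up to 9 scores), fit one linear mixed model with group, visit and group-by-visit and an unstructured within-patient covariance. Report the between-group mean difference with its 95% interval at each visit and averaged over visits. Allow statements about change over time only from the group-by-visit term, noting that a non-significant result does not show a constant effect. Keep Mann-Whitney only as a sensitivity check, not described as comparing means. No scale score before discharge is described, so the model should use the three follow-up visits. Define IUBÖ. If outcome results are already known, label the model post hoc.

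The cost is a modest reanalysis and a rewritten paragraph. The downsides are:
- modelling assumptions on bounded scores (in five assumed skewed shapes the ordinary two-sample interval still covered 94–95%, but the mixed model itself was not tested);
- little gain in precision at single visits;
- low power of the group-by-visit test;
- a visit average that is weaker than the 6-month test if the effect builds late.

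### MARS and MIDAS are compared by unadjusted two-sample tests although pre-discharge characteristics are collected from every patient; the tests are valid on average, but precision and protection against chance imbalance are given up

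*Combined protocol and SAP*

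**What the plan says.** In the combined protocol and SAP, Data Analysis is the whole statistical plan. A Kolmogorov–Smirnov test decides between two score comparisons: "Student's t test was used to compare the mean scores that showed normal distribution", and Mann-Whitney U for the rest. Nominal variables are compared between groups by chi-square or Fisher-Freeman-Halton tests. No regression, analysis of covariance, mixed model, covariate list or rule for imbalance appears.

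Three other places bear on this:

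- Study design and sample: allocation "was made using the simple randomization method". No strata, blocks or minimization are described. There were 30 completers in the intervention arm and 31 in the control arm.
- Mobile application and web page control panel: "the Patient Information Form was filled out with all patients in the patient room before discharge". The scales are placed only at 1, 3 and 6 months, so no pre-discharge MARS or MIDAS score is described.
- Data collection tool: the form "consists of questions about the socio-demographic, the lifestyle, and the disease characteristics of the participants".

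**The concern.** Candidate prognostic variables are in hand for every patient, and none enters a score comparison. Simple randomization with about 30 per arm balances nothing by design, so the analysis is the only place left to allow for a chance difference in a factor that predicts adherence or quality of life.

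Two things are at stake. If such a factor differs between arms in the trial obtained, the unadjusted difference is shifted by the factor's effect and the error rate for that trial is no longer 5%. Even with good balance, outcome variation that the covariates could explain stays in the standard error.

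**Working it through.** **Inputs from the documents.** "The effect size of the study was found to be 0.92", read here as a standardized mean difference because the outcome and SD are not named; "sufficient to include a total of 54 patients, 27 in each group", "at 95% power and 0.05 significance level"; 30 v 31 completers; threshold p<0.05, side not stated.

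**Assumption.** Three independent covariates with equal weight jointly explain R² = 0.1, 0.2 or 0.3 of the score variance. The documents give no value.

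**1. The plan's own figure.** By noncentral t, 27 per arm at d = 0.92 gives 95.5% power one-sided, and 26 gives 94.8%. So 54 reproduces exactly as a one-sided, unadjusted t test. Two-sided, 27 per arm gives 91.3%, and 32 per arm are needed for 95%. Everything below is two-sided at 30 v 31.

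**2. Chance imbalance.**

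- The SD of a standardized difference is √(1/30 + 1/31) = 0.256.
- For one covariate, P(|difference| > 0.4 SD) = 2 × (1 − Φ(0.4/0.256)) = 11.8%.
- For at least one of three, 1 − (1 − 0.118)³ = 31%.
- The combined prognostic score is a single variable, so its probability is again about 12%.

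**3. Precision.** The ratio of adjusted to unadjusted standard error is √[(1 − R²)(1 + 3/55)]. The second factor is the cost of estimating three covariates with 61 patients (61 − 2 − 3 − 1 = 55). Break-even is R² = 1 − 1/(1 + 3/55) = 5%.

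**4. Results.** Unadjusted power is 94% at 0.92 SD and 80% at 0.73 SD. The last two columns are simulated rejection rates of the unadjusted t test with no app effect.

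| R² | SE ratio | Adjusted power, 0.92 SD | Adjusted power, 0.73 SD | Any of three covariates off >0.4 SD (31% of trials) | Combined score off >0.4 SD (12% of trials) |
|---|---|---|---|---|---|
| 0 | 1.027 | 93% | 78% | 5% | 5% |
| 0.1 | 0.974 | 95% | 82% | 6% | 9% |
| 0.2 | 0.918 | 97% | 86% | 7% | 12% |
| 0.3 | 0.859 | 98% | 90% | 8–9% | about 16% |

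Over all simulated trials, both the unadjusted and the adjusted test reject 5% of the time. Given either imbalance, the adjusted test stays near 5%. At R² = 0.3 the simulated values varied a little between runs: 7.9% to about 9% in the fifth column, and 15.1% to 16.3% in the last.

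**5. Hand check of the conditional error.** Take one covariate with outcome correlation 0.5 (assumed), out of balance by 0.5 SD.

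- The unadjusted difference shifts by 0.5 × 0.5 = 0.25 SD, which is 27% of 0.92.
- Given that imbalance, its standard error is 0.256 × √(1 − 0.25) = 0.222.
- Upper tail: (1.96 × 0.256 − 0.25)/0.222 = 1.14, probability 12.8%. The lower tail is negligible.

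**The case against.** The strongest reply is that this is a matter of efficiency in a valid analysis. Most of that stands.

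- **Validity.** A reader might infer that the unadjusted tests are wrong. They are not: over all randomizations they hold 5%.
- **Actual imbalance.** A reader might infer that the arms differed. The text has no baseline table or arm-level characteristics, so only probabilities can be given.
- **Baseline testing.** A reader might infer that pre-discharge characteristics are significance-tested between arms. Data Analysis speaks only of nominal variables, and the same form is completed again at follow-up, so the documents do not establish that use.
- **Size.** It is tempting to set the 9/12/16% error rates beside the 31% probability. They belong to different events: 31% goes with about 6/7/8–9%, and 9/12/16% goes with 12%. At the planned 0.92 SD the power gain is only 1 to 4 points.
- **Covariates.** The form is described by broad domains, so which items exist and how well they predict the scores are unknown. Below R² of about 5%, adjustment costs slightly more than it returns.
- **Scale and test.** MARS runs from 5 to 25 and may be skewed or at its ceiling. The calculations concern the t test, so no gain over Mann-Whitney is shown.
- **Timing.** Follow-up is complete and the text reports reliability figures from this study's data. Covariates may no longer be choosable blind to the arm comparison.

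What survives is that no covariate enters any score comparison, that neither design nor analysis deals with chance imbalance, and that the data to do so are already collected.

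**Conclusion.** The point holds as a recommended improvement, not as a demonstrated error. The unadjusted comparisons are valid on average. They forgo 3/8/14% of the standard error if three pre-discharge covariates explain 10/20/30% of score variance, and they leave the trial obtained exposed if a prognostic factor is out of balance. The downside of adjusting is about 3% on the standard error.

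The sizes rest on the assumed R², on three equally weighted, independent covariates, on roughly normal scores and on two-sided testing. The gain matters more if the true effect is below 0.92 SD. The documents do not support the conclusion that any result is biased, or that an imbalance occurred.

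**What to change.** In Data Analysis, add for each scale a linear model of the score on arm plus two or three pre-discharge covariates from the Patient Information Form, for example age. Choose them on prognostic grounds, not by a between-arm p-value. Then:

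- Report the adjusted difference with a 95% CI, and the unadjusted t or Mann-Whitney result alongside.
- Where a score is skewed or at its ceiling, as MARS may be, use robust or bootstrap standard errors, or a rank-based or ordinal model that takes covariates.
- If the arms have already been compared, label the adjusted model a post hoc sensitivity analysis.
- If the chi-square or exact tests are applied to pre-discharge characteristics, do not let them decide whether to adjust.

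The cost is a few sentences in the plan, one extra model per scale on data already collected, and two or three degrees of freedom.

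### Repeated lifestyle and disease items have a pre-discharge value, but the only tests named for nominal variables would ignore it at follow-up

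*Combined protocol and SAP*

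**What the plan says.** **When the form is completed.** Under Study Protocol (Mobile application and web page control panel), "the Patient Information Form was filled out with all patients in the patient room before discharge". Both arms then had follow-up visits "1 month, 3 months and 6 months after discharge, and the Patient Information Form, IUBÖ ve MIDAS scales were filled out". Only the form is named at the pre-discharge step; the scales appear only at follow-up.

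**What the form holds.** Under Data collection tool, it "consists of questions about the socio-demographic, the lifestyle, and the disease characteristics of the participants".

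**How arms are compared.** Data Analysis gives Student's t or Mann-Whitney U for scores. For categorical data it gives Pearson chi-square and Fisher-Freeman-Halton tests, which "were used to determine the relationship between groups for nominal variables". It describes no covariate, stratified, paired, change or repeated-measures method, and lists no variables or visits.

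**How arms were formed.** Under Study design and sample, allocation "was made using the simple randomization method", with no stratification described. The study was completed with 30 intervention and 31 control patients.

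**The concern.** A lifestyle item recorded before discharge and at follow-up has a true pre-intervention value. An arm-by-category table at 6 months does not use it. For a yes/no item, a patient who never had the habit then counts the same as one who gave it up, and any starting difference between arms carries into the comparison.

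With about 30 patients per arm and no stratification, sizeable starting differences will occur by chance for some items. Two things are at stake. One is the reading of a particular result: did the app change behaviour, or did the arms start apart? The other is precision, where the pre-discharge answer is a good predictor. Lifestyle is relevant to the intervention, because the app has a lifestyle section and sends personalized reminders drawn from the booklet.

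**Working it through.** **The plan's own figure.** No planning figure exists for the nominal items. The only one is "a total of 54 patients, 27 in each group, at 95% power and 0.05 significance level". If the effect size of 0.92 is read as a standardised mean difference, a one-sided t-test reproduces 27 per group (power 95.5%). Two-sided, 27 per group gives 91.3%. That is a separate matter and says nothing about categorical items.

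**Inputs from the documents.** 30 v 31 patients, simple randomization, significance limit 0.05.

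**Assumptions, because the documents give no rates.** A yes/no habit; prevalence before discharge p = 30–60%; 70% of those with the habit keep it in the control arm; 0–10% of the others take it up.

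**Step 1: chance gap before discharge.** SD = √[p(1−p)(1/30 + 1/31)], with 1/30 + 1/31 = 0.0656. The chance of a gap above 20 points is 2[1 − Φ(0.20/SD)].

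| p | SD | P(gap > 20 points) |
|---|---|---|
| 30% | √(0.21 × 0.0656) = 0.117 | 8.8% |
| 50% | √(0.25 × 0.0656) = 0.128 | 11.8% |
| 60% | √(0.24 × 0.0656) = 0.125 | 11.1% |

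So about 9–12% (binomial simulation gives 9–13%).

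**Step 2: how the gap carries over.** With no app effect, the expected follow-up gap is (persistence − uptake) × starting gap. A 20-point start becomes 0.70 × 20 = 14 points with no uptake, or 0.60 × 20 = 12 points with 10% uptake.

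**Step 3: the two tests.**
- Unadjusted: X² = d² / [p̄(1−p̄)(1/30 + 1/31)], where d is the difference in follow-up proportions and p̄ the pooled proportion.
- Stratified (Mantel-Haenszel, no continuity correction): [Σ(e − m₁t/N)]² / Σ{m₁m₀t(N−t) / [N²(N−1)]}, summed over pre-discharge categories. Here e is intervention patients with the habit at follow-up, t is all patients with it, m₁ and m₀ are the arm sizes, and N = m₁ + m₀.

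**Step 4: no app effect (simulated).**

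| | Chi-square | Stratified |
|---|---|---|
| All trials | 4.8–5.6% | 4.3–5.0% |
| Starting gap > 20 points | about 17–33% | about 4–6% |

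The overall rate holds because the remaining trials reject only 2.6–3.7% of the time under chi-square. The range of 17–33% spans scenarios. At 50% prevalence it is roughly a fifth to a quarter. Values above 30% arise only at 30% prevalence with no uptake, where about 9% of trials start that far apart.

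**Step 5: power at 50% prevalence.** The correlation between pre-discharge and follow-up answers in the control arm is φ = (persistence − uptake) × √[p(1−p)] / √[q(1−q)], with q the follow-up prevalence. For 70% and 10%, q = 0.40 and φ = 0.60 × 0.5/0.490 = 0.61. For 70% and 0%, q = 0.35 and φ = 0.73. For 40% and 10%, q = 0.25 and φ = 0.35. For 30% and 10%, q = 0.20 and φ = 0.25.

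| Stopping, app v control | Uptake | φ | Chi-square | Stratified |
|---|---|---|---|---|
| 60% v 30% | 0% | 0.73 | 26% | 37% |
| 60% v 30% | 10% | 0.61 | 25% | 30% |
| 70% v 30% | 0% | 0.73 | 45% | 60% |
| 70% v 30% | 10% | 0.61 | 40% | 47% |
| 85% v 60% | 10% | 0.35 | 25% | 24% |
| 90% v 70% | 10% | 0.25 | 21% | 19% |

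**Step 6: version of the stratified test.** In the first row, a continuity-corrected Mantel-Haenszel test has about 24% power, below chi-square at 26%, and an exact stratified test about 31%. The gain therefore depends on the version chosen.

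**The case against.** The case against is substantial, and most of it stands as a limit on the point.

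- **Use at follow-up is inferred.** A reader might take the plan to say that lifestyle items are compared by chi-square at each visit. It does not. The tests could be meant only to describe the arms at entry. What stands is that no other method is named for nominal data. If these tests were for entry only, the repeated items have no planned analysis, and a sentence is still needed.
- **Lifestyle is not a named outcome.** The aim covers treatment adherence, self-management and quality of life. Self-management has no scale described, so a reader might infer that the form's lifestyle items serve as that outcome. No text says so. Both arms also received the booklet that the app's lifestyle section repeats.
- **The items themselves are not shown.** If an item has never, former and current categories, the ordinary table already separates never from former.
- **Randomization already covers chance imbalance.** A reader might infer that the chi-square test is biased or has an inflated error rate. It does not: the overall rate is about 5%. The excess is conditional on a large gap having occurred.
- **The power gain rests on assumed strong persistence.** The last two rows of the power table show none, or a slight loss.

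Nor does the point extend to the adherence and quality-of-life scales, since the text describes no pre-discharge value for them.

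**Conclusion.** The point holds as a specific, inexpensive improvement and not as an invalid analysis. A pre-discharge answer is on file for items that can change, and the only methods named for nominal data do not use it.

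If those methods are applied at follow-up, the cost is twofold. First, in the roughly 9–12% of trials that start more than 20 points apart, rejection with no app effect is about 17–33% against 4–6% when stratified. Second, power is lost where the pre-discharge answer predicts well: about 5 to 15 points in the strong-prediction scenarios, and nothing where it predicts weakly.

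All these sizes rest on assumed prevalence, persistence and uptake for a yes/no item. The documents give no such rates and do not report whether any imbalance occurred.

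**What to change.** In Data Analysis:

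1. List which form items are compared between arms, and at which visits.
2. For each lifestyle or disease item that can change and is recorded both before discharge and at follow-up, compare arms with a Mantel-Haenszel (Cochran) test stratified by pre-discharge category. State that no continuity correction is used. Report the common odds ratio with a 95% CI. For items with more than two categories, name the category contrast in advance.
3. Where strata are sparse, or a logistic model would separate (for example, when nobody takes a habit up), use an exact or mid-p stratified test.
4. Keep Pearson chi-square and Fisher-Freeman-Halton for items with no pre-discharge value and for describing the arms at entry.
5. Label these comparisons secondary.

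**Cost.** A few lines of analysis text and a re-run on data already collected. The downsides are little or no power gain, or a slight loss, for items weakly related to their pre-discharge value, and conservative exact tests for rare habits.
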